#### **7.1.2.3.3. Causality**

The Investigator will assess the causality/relationship between the IMP and the AE and record that assessment in the CRF. The most likely cause of an AE/SAE (e.g., disease under treatment, concomitant disease, concomitant medication, other) will be indicated in the CRF with details of the concomitant disease, medication, or other cause.

The causal relationship of the AE to IMP will be described in terms of:

- Possible: the AE:
  - Follows a reasonable temporal sequence from administration of the IMP

- Could be reasonably explained by the patient's clinical state, environmental or toxic factors or other therapies administered to the patient
- Follows a known pattern of response to the IMP
- Unlikely: the AE:
  - Does not follow a reasonable temporal sequence from administration of the IMP
  - Could be reasonably explained by the patient's clinical state, environmental or toxic factors, or other therapies administered to the patient
  - Does not follow a known pattern of response to the IMP
  - Does not reappear or worsen upon re-challenge
- Not related:
  - The AE does not meet the above criteria
  - There is sufficient information that the aetiology of the AE is not related to the IMP

The relatedness of SAEs will also be assessed and documented on the appropriate CRF page.

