#### **7.1.2.4. Recording of Adverse Events**

Adverse events will be collected from the time a patient signs the ICF until the Follow-up Visit.

All AEs, regardless of the relationship to IMP, must be recorded in the source documents (e.g., medical record) and will be recorded on the appropriate CRF pages, and documents provided by the Sponsor.

All AE reports should contain a brief description of the event, date, and time of onset, date and time of resolution, intensity, treatment required, relationship to IMP, action taken with the IMP, outcome, and whether the event is classified as serious.

Serious adverse events should be collected for up to 30 days after the last dose of the IMP for subjects unless the subject has withdrawn consent. This could be collected as a phone call.

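### The causality scale has no grade for an adverse event without another explanation, and its residual bullet can send a well-timed, known-pattern, recurring event to Not related

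*Protocol*

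**What the plan says.** Protocol 7.1.2.3.3 asks the investigator to choose one of three grades.

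- **Possible** lists a reasonable temporal sequence, an alternative explanation ("Could be reasonably explained by the patient's clinical state, environmental or toxic factors or other therapies administered to the patient") and a known pattern ("Follows a known pattern of response to the IMP").
- **Unlikely** lists the absence of a temporal sequence, the same alternative-explanation feature, the absence of a known pattern, and "Does not reappear or worsen upon re-challenge".
- **Not related** lists "The AE does not meet the above criteria" and "There is sufficient information that the aetiology of the AE is not related to the IMP".

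None of the three lists says whether all of its bullets are needed or one is enough. The same section separately requires a probable cause: "The most likely cause of an AE/SAE (e.g., disease under treatment, concomitant disease, concomitant medication, other) will be indicated in the CRF". Protocol 7.1.2.4 adds that "All AEs, regardless of the relationship to IMP, must be recorded in the source documents". SAP 9.3.1 plans an overview row and a System Organ Class table by relationship to SNF472, without a definition of its own.

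**The concern.** The feature that should separate a probable drug reaction from a doubtful one is whether something else could explain the event. Here that feature sits in both Possible and Unlikely, so it does not separate them, and its absence is described nowhere. Positive re-challenge is also missing: recurrence appears only in the negative, under Unlikely. It is relevant here because up to 36 infusions are planned per patient, so re-exposure after an event is built into the schedule.

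An event with the strongest evidence for the drug (good timing, known pattern, recurrence, nothing else to explain it) therefore matches no grade in full, and the only bullet written for unmatched events lies in the lowest grade. At stake is the relatedness label in the SAP tables, in the minimum content of an SAE report (Protocol 7.1.2.5) and in the association judgement on which SUSAR reporting turns (Protocol 7.1.2.7). SAP 8.6 expects 1 to 2 subjects per site, so 15 subjects would mean at least 8 sites (15/2 = 7.5), each applying an unstated rule.

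**Working it through.** The plan gives no figure to reproduce. The check is a truth table over four yes/no features taken from the bullets of Protocol 7.1.2.3.3:

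- T = reasonable timing
- O = other reasonable explanation
- K = known pattern
- R = recurs on re-challenge

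These give 2 × 2 × 2 × 2 = 16 combinations. Sufficient information of another aetiology is set to no throughout.

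**Formulas**

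- Possible, all bullets: T and O and K, 2 of 16. Any bullet: T or O or K, 14 of 16.
- Unlikely, all bullets: not T and O and not K and not R, 1 of 16. Any bullet: not T or O or not K or not R, 15 of 16.
- Not related, either bullet: every combination meeting neither Possible nor Unlikely. Both bullets: none, because sufficient information is set to no.

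**Results for the 2 × 2 × 2 = 8 readings.** The key event is T, not O, K, R.

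| Possible | Unlikely | Not related | Possible only | Unlikely only | Both of these | Not related | No grade | Key event |
|---|---|---|---|---|---|---|---|---|
| all | all | either | 2 | 1 | 0 | 13 | 0 | Not related |
| all | all | both | 2 | 1 | 0 | 0 | 13 | no grade |
| all | any | either | 0 | 13 | 2 | 1 | 0 | Not related |
| all | any | both | 0 | 13 | 2 | 0 | 1 | no grade |
| any | all | either | 13 | 0 | 1 | 2 | 0 | Possible |
| any | all | both | 13 | 0 | 1 | 0 | 2 | Possible |
| any | any | either | 1 | 2 | 13 | 0 | 0 | Possible |
| any | any | both | 1 | 2 | 13 | 0 | 0 | Possible |

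In the any/any rows the overlap is 14 + 15 − 16 = 13.

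**The first row in detail.** Not related receives 16 − 2 − 1 = 13 combinations. Possible and Unlikely both require O, so all 8 combinations without another explanation are among them. The other 5 have another explanation (8 − 2 − 1 = 5); they include both well-timed combinations with no known pattern. Of the 13, 3 have neither timing nor recurrence, so a low grade is reasonable for them. The other 10 have timing or recurrence or both.

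**Re-challenge not done.** If R can also be not done, there are 24 combinations. The first row becomes 3 Possible, 1 Unlikely and 24 − 3 − 1 = 20 Not related. Under any/any, 19 meet both Possible and Unlikely.

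These are logical combinations, not event rates. The documents do not allow the number of real events affected to be estimated.

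**The case against.** The strongest reply is that causality is a clinical judgement. The bullets describe each grade and are not an algorithm, and an investigator who graded the key event Not related would be passing over the second Not related bullet, which asks for positive information. The CRF is not among the documents and may carry instructions. This stands in part: the wrong label is possible, not certain. But the section presents the bullets as criteria, its residual bullet refers back to them as such, and nothing in the protocol or SAP supplies another rule.

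A reader might infer that no reading gives every combination exactly one grade. That is not so: the first row of the table does. Its fault is where it puts them. A reader might also infer that the key event must end as Not related. It does so in 2 of 8 readings, and only if Possible needs all its bullets while one Not related bullet is enough.

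It is also fair to say that the safeguards are good. The most likely cause is recorded separately, all AEs are recorded, all SAEs go to pharmacovigilance within 24 hours whatever their association, an independent medical monitor reviews the totality of safety information (Protocol 7.1.2.8), and SAP 8.1 lists the data. These protect capture and review of events. They do not correct the grade itself.

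**Conclusion.** The concern holds as a defect in the relatedness label. On the one reading that grades every combination once, 13 of 16 go to Not related, including all 8 with no other explanation. On each of the other seven readings, some combinations meet both Possible and Unlikely or have no grade, up to 13 of 16.

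The effect reaches the two relationship outputs in SAP 9.3.1, the investigator causality field in SAE reports, and the association judgement for SUSARs. For SUSARs the protocol does not say how association is decided, so that the grade feeds it is an assumption, though a natural one. AE capture, 24-hour SAE reporting, the all-causality tables and the efficacy endpoints are untouched.

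The documents do not support the stronger conclusion that every well-timed event should be at least Possible. With three infusions a week for 12 weeks, timing alone could fit a large share of events, and Protocol 7.2 records dialysis-related events separately. The conclusion assumes that the CRF adds no combining rule.

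**What to change.** In Protocol 7.1.2.3.3 and the CRF:

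1. Delete the residual bullet, so that Not related requires sufficient information that the aetiology is not the IMP.
2. State for each grade how its bullets combine.
3. Provide that a well-timed or recurring event with no other reasonable explanation is graded at least Possible, or in an added Probable/Related grade. For Possible, another explanation is then allowed but not required.

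Step 3 settles 6 of the 8 combinations without another explanation (3 of the 4 timing-by-recurrence patterns, each with or without a known pattern). The other 2 have neither timing nor recurrence, and the rule from step 2 must place them explicitly once the residual bullet is gone. The grade of a well-timed event that does have another explanation stays with the investigator's judgement.

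The cost is wording in the protocol and CRF, an unknown number of additional events labelled possibly related, and re-grading or a stated mapping for events already graded.

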#### **7.1.2.4. Recording of Adverse Events**

Adverse events will be collected from the time a patient signs the ICF until the Follow-up Visit.

All AEs, regardless of the relationship to IMP, must be recorded in the source documents (e.g., medical record) and will be recorded on the appropriate CRF pages, and documents provided by the Sponsor.

All AE reports should contain a brief description of the event, date, and time of onset, date and time of resolution, intensity, treatment required, relationship to IMP, action taken with the IMP, outcome, and whether the event is classified as serious.

Serious adverse events should be collected for up to 30 days after the last dose of the IMP for subjects unless the subject has withdrawn consent. This could be collected as a phone call.

#### **7.1.2.5. Reporting of Serious Adverse Events**

All SAEs that occur during the period of observation (from the first administration of the IMP until the Follow-up Visit) whether considered to be associated with the IMP or not, must be reported within 24 hours after knowledge of the SAE by email or fax to the Pharmacovigilance Department.

The minimal information required for an initial report is:

- Sender of report (name, address of Investigator)
- Protocol number
- Patient identification (Patient ID, initials, NOT patient name)
- Full description of SAE
- Details of the IMP
- Investigator Causality assessment

However, as far as possible all points on the SAE form should be covered in the initial report and the completed SAE form must be emailed to the Pharmacovigilance Department ( [REDACTED] ). In addition, the SAE must be documented in the CRF and documents provided by the Sponsor.

In case the Pharmacovigilance Department cannot be contacted (e.g., after business hours or on weekends), an automated reporting service is available. The required information should be faxed and a message should be left on the voicemail service.

A 24-hour emergency contact will be available during the conduct of the clinical trial. For medical emergencies, the following phone number will be available:

[REDACTED]

[REDACTED]

After receipt of the initial report, the Pharmacovigilance Department will review the information and, if necessary, contact the Investigator to obtain further information for assessment of the event. The Investigator will be responsible for informing the local Ethics committee (EC)/ Independent Review Boards (IRB), and central IRB as per local EC/IRB and central IRB requirements. The Sponsor, will be responsible for informing all Regulatory Authorities and the Investigators (if applicable), of findings that could adversely affect the safety of subjects or impact the conduct of the study and will report to regulatory authorities in conformity with expedited and periodic reporting requirements.

Details for the reporting of Suspected Unexpected Serious Adverse Reactions (SUSARs) can be found in Section 7.1.2.7.

#### **7.1.2.6. Follow-up of Adverse Events**

All AEs experienced by a patient, irrespective of the suspected causality, will be monitored until the event has resolved, any abnormal laboratory values have returned to baseline or stabilised at a level acceptable to the Investigator and Medical Monitor, until there is a satisfactory explanation for the changes observed, or until the patient is lost to follow-up.

#### **7.1.2.7. Suspected Unexpected Serious Adverse Reactions**

Any AE that is serious or associated with the use of the IMP and SUSARs have additional reporting requirements, as described below:

- If the SUSAR is fatal or life-threatening, associated with the use of the IMP, and unexpected, Regulatory Authorities, the EC/IRB, and Investigators will be notified within 7 calendar days after the Sponsor learns of the serious adverse event. Additional follow-up (cause of death, autopsy report, hospital report) information will be reported within an additional 8 days (15 days in total)
- If the SUSAR is not fatal or life-threatening but is otherwise serious, associated with the use of the IMP, and unexpected, Regulatory Authorities, the EC/IRB and the Investigators will be notified within 15 calendar days after the Sponsor learns of the serious adverse event

The Sponsor will also provide annual safety reports to the Regulatory Authorities and the EC responsible for the clinical trial. These updates will include information on SUSARs and other relevant safety findings.

#### **7.1.2.8. Periodic Independent Safety Monitoring**

An independent medical monitor will evaluate the totality of safety information collected in the trial at the following time points: 1) when the first 5 patients have completed a full 12 weeks of treatment; 2) when the first 10 patients have completed a full 12 weeks of treatment; and at End of Study. The independent medical monitor will be appointed prior to the first time point and will be a qualified individual who is not directly involved in study conduct and is not a direct employee of the Sponsor or any Principle Investigator in the study.

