## 2.2. Rationale for the Clinical Trial

CUA patients are almost all on dialysis, except for a very small percentage who are non-uraemic. CUA has no specific treatment. Calciphylaxis is a life-threatening condition with a high mortality rate. The overall mortality in calciphylaxis patients with ESRD is 60-80% with a 1 year survival of 45% [35, 36], whereas non-uremic calciphylaxis appears to have a slightly better prognosis with an overall mortality of 52% [37].

The difference between survival curves of cases and controls was most striking in the first year and more specifically in the first few months after the diagnosis of calciphylaxis [38]. It is clear that the progression of calciphylaxis is highly aggressive with early mortality compared to HD patients without calciphylaxis. The mortality of non-uraemic calciphylaxis seems to be about 30% lower than in patients with uraemic calciphylaxis [36, 37].

The pathophysiology of CUA involves the deposition of calcium in the media of small vessels. This leads to regional, extremely painful ischemia leading to ulceration. The lesions tend to appear in the upper and lower limbs, although truncal lesions have also been described. In addition to the pain – requiring opioids to be managed – these patients have an increased susceptibility to infections, which is responsible for over 50% of the mortality. Empirical treatments available include sodium thiosulfate, hyperbaric O2, bisphosphonates, surgical debridement, and other locally implemented initiatives. However, these measures do not seem to improve either the course of the wound(s) or the high mortality rate [39-42]. SNF472, due to its innovative mechanism of inhibition of the final common pathway of vascular calcification, has the potential to decrease the amount of vascular calcification in these patients, hence shortening the time to healing of the wounds and potentially decreasing mortality rates. This study will address the potential of SNF472 to improve the course of the wounds seen in CUA patients.

Further details can be found in the Investigator's Brochure [26].

See Section 4.3 for justification of the clinical trial design.

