### 5.1. Number of Patients

It is planned to include 15 male or female CUA patients who complete the 12-week treatment period.

Patients who leave the clinical trial before being entered into the study will be considered as screening failures and will always be replaced. Therefore, sufficient reserve patients should be recruited, where possible. Patients withdrawn after dosing may be replaced as needed to obtain 15 patients who complete the 12-week treatment period.

See Section 9.5 for a discussion of sample size.

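### Both independent safety reviews during the trial wait for 12-week completers, so deaths and early withdrawals postpone them

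*Protocol*

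**What the plan says.** Protocol 7.1.2.8 gives an independent medical monitor three reviews. The first falls "when the first 5 patients have completed a full 12 weeks of treatment". The other two fall "when the first 10 patients have completed a full 12 weeks of treatment; and at End of Study". At each one the monitor "will evaluate the totality of safety information collected in the trial", so patients who did not complete are included once a review takes place. The section also says: "The independent medical monitor will be appointed prior to the first time point". Nothing in it starts a review on a death, a serious adverse event, a withdrawal, a number of patients dosed or elapsed time.

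Protocol 5.1 provides for replacement: "Patients withdrawn after dosing may be replaced as needed to obtain 15 patients who complete the 12-week treatment period". SAP 6.1 instead describes an enrolment of up to 15 subjects.

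On background risk, Protocol 2.2 states "The overall mortality in calciphylaxis patients with ESRD is 60-80% with a 1 year survival of 45" per cent. It adds that the survival difference from controls was "most striking in the first year and more specifically in the first few months after the diagnosis of calciphylaxis".

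**The concern.** Under this rule a patient who dies in Week 3 leaves the completer count where it was, and may be replaced. The more patients are lost early, the more must be dosed, and the longer the wait, before the monitor looks. The timing of the review therefore moves in the wrong direction with harm.

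This matters here for three reasons.
- Inclusion criterion 1 requires a new or recurrent diagnosis within 5 weeks of study start, so patients enter in the period when the protocol itself says excess mortality is most marked.
- There is no control arm. Deaths from infection may be put down to the disease case by case, so an excess would have to be recognised in the accumulating data.
- The monitor need only be appointed before the first completer-based time point, so none need be in post while the first losses accrue.

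The wording has a second reading. If the first 5 patients means the first 5 enrolled, a single early death among them makes the condition impossible to meet as written.

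**Working it through.** The documents give no calculation behind the review schedule, so there is no figure of theirs to reproduce on this point. The check asks how far the two reviews move as losses rise.

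**Inputs from the documents.** Triggers at 5 and 10 completers and a 12-week treatment period (Protocol 7.1.2.8); one-year survival of 45% (Protocol 2.2); replacement until 15 complete (Protocol 5.1); up to 15 enrolled (SAP 6.1).

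**Assumptions.** The documents give neither the accrual rate nor the 12-week loss rate. Accrual is taken as 0.5, 1 or 2 patients per month. SAP 7.1 mentions difficulty in finding qualifying subjects, and SAP 8.6 expects 1 to 2 per site, so slow accrual is plausible. Loss is taken as 0%, the rate implied by the quoted survival, and 40% as a stress case.

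**Step 1: loss by 12 weeks at a constant hazard.** 1 − 0.45^(12/52) = 0.168, so the completion probability is p = 0.832. The error can go either way. Mortality concentrated in the first months would raise the loss, as would withdrawals for other reasons. Exclusion criterion 4 (no reasonable expectation of survival beyond 6 months) would lower it.

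**Step 2: patients who must be dosed for 5 completers, on average 5/p.**
- No loss: 5.0
- 16.8% loss: 5/0.832 = 6.0, about 1 of them lost
- 40% loss: 5/0.60 = 8.3, about 3.3 of them lost

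**Step 3: expected time of the review, in weeks from the opening of enrolment.** With r patients per month, arrivals are on average (52/12)/r weeks apart. The k-th completion then falls at (k/p) × (52/12)/r + 12. For the first review at 1 per month:
- No loss: 5.0 × 4.33 + 12 = 33.7
- 16.8% loss: 6.01 × 4.33 + 12 = 38.1, a slip of 4.4 weeks
- 40% loss: 8.33 × 4.33 + 12 = 48.1, a slip of 14.4 weeks

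| Review and accrual | No loss | 16.8% loss | 40% loss |
|---|---|---|---|
| First, 0.5/month | 55.3 | 64.1 | 84.2 |
| First, 1/month | 33.7 | 38.1 | 48.1 |
| First, 2/month | 22.8 | 25.0 | 30.1 |
| Second, 1/month | 55.3 | 64.1 | 84.2 |

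Simulation with random arrivals agreed with these times. At 1 per month, an average of 1.3 early exits at 17% loss, and 3.9 at 40% loss, had already occurred when the first review fell due.

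**Step 4: can the second review be missed?** Under Protocol 5.1, replacement continues until 15 complete, so 10 completers are reached if that plan is met. If the SAP's limit of 15 enrolled applied instead, the chance of fewer than 10 completers is P(Bin(15, p) < 10):
- 16.8% loss: 1 − 0.972 = 0.03
- 35% loss (assumed): 1 − 0.564 = 0.44
- 40% loss (assumed): 1 − 0.403 = 0.60

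**Step 5: the alternative trigger.** Suppose the review falls when each of the first 5 dosed patients has completed 12 weeks or left treatment. It then comes no later than 12 weeks after the fifth patient starts, which is 33.7 weeks on average at 1 per month whatever the loss. It cannot be later than the present trigger, because the fifth completer starts no earlier than the fifth patient dosed. With no losses the two coincide.

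**The case against.** The strongest reply is that this is one channel among several. Serious adverse events go to the Pharmacovigilance Department within 24 hours whatever their cause (7.1.2.5). Suspected unexpected serious reactions go to regulators, ethics committees and investigators within 7 or 15 days (7.1.2.7). Clinically relevant safety issues prompt notification (10.12), and the sponsor or regulators may request termination (5.5). The trial is open label, so each event is seen unmasked. This stands: a reader might infer that harm would go unseen, and the documents do not support that. These channels still do not amount to an independent look at all accumulating data. The SAP 7.1 interim analysis does not fill the gap either, because it too waits for completers and its stated aims are enrolment and future design.

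A reader might also infer that data from patients who die or withdraw escape review, or that no independent review is certain. Neither follows. Each review takes in all safety information, and the End of Study review is set regardless of completions.

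A third tempting inference is that the second review may never happen. That needs the SAP's enrolment limit to override the protocol's replacement rule, and it becomes likely only at loss rates that the documents do not give.

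Finally, waiting for a fixed number of full 12-week exposures can be defended, since earlier exposure in haemodialysis patients was up to 28 days (Protocol 2.3). The protocol does not offer this rationale. It is nevertheless a real trade-off, and it is the main cost of the change.

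**Conclusion.** The point holds for the two independent reviews that take place during the trial: deaths and early withdrawals postpone them. The direction is the same at every accrual rate tried. At the one loss rate that can be derived from the documents (16.8%, constant hazard) the slip is modest, about 4 weeks at 1 patient per month and about 9 weeks at 0.5 per month. At an assumed 40% loss it is about 14 weeks at 1 per month. The delay is thus large only when losses are heavy, which is when an independent look is most needed.

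The point does not extend to safety oversight as a whole, to loss of data or to the End of Study review. The risk of missing the second review is conditional on the conflict between Protocol 5.1 and SAP 6.1. This is a cheap improvement to the design, not an error that invalidates it.

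**What to change.** Reword the first two triggers in Protocol 7.1.2.8 along these lines: the monitor reviews all safety data when each of the first 5, and then the first 10, dosed patients has either completed 12 weeks or left treatment for any reason, including death. Keep the End of Study review. Separately, reconcile the protocol's 15 completers with replacement and the SAP's limit of 15 enrolled.

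The cost is one sentence, with no added reviews or staff. Each review would hold fewer full 12-week exposures: of the first 5 dosed, on average 5 × 0.832 = 4.2 at 16.8% loss and 5 × 0.60 = 3 at 40%. The change removes the extra delay caused by losses. It does not make a cluster of early deaths bring a review forward on its own, because the review still waits for the remaining patients among the first 5 to finish or leave.
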